## **15.2.2 Best Overall Response and Objective Response**

*Analysis sets: FAS, PP, HRQoL Analysis Set*

The confirmed BOR is defined as the best confirmed response obtained among all tumor assessment visits completed after the date of randomization until documented disease progression. Requirements for confirmation of responses is detailed below. The tumor response at each assessment visit will be determined according to RECIST 1.1, as assessed by the investigator relative to the Re-Baseline scan.

Only tumor assessments performed on or before the start of any further anti-cancer treatment will be considered in the assessment of BOR. Clinical deterioration (“progressive disease based on clinical assessment” as captured on the treatment discontinuation eCRF pages) will not be considered as documented disease progression in the context of BOR/tumor response.

Subjects without measurable disease at the Re-Baseline visit (i.e. subjects who experienced a complete response at completion of the Induction Phase) may have subsequent tumor assessments which show no evidence of disease (i.e. no new lesions, no non-target lesions, sum of diameters of

---

the target lesion  $\leq 5$  mm). In such cases, these patients will be assigned a timepoint response of No Evidence of Disease (NED), however a timepoint response of NED is not a valid response for use as a Best Overall Response. Therefore, these subjects cannot achieve a BOR other than NE or PD, and these subjects will be included in the analysis as non-responders. For subjects who have a timepoint Overall Response of NED which occurs at least 42 days after randomization, BOR will be defined as NE with reason "NED maintained post Re-Baseline". Scans showing NED within the 42 day window will not be considered for purposes of BOR determination.

The following requirement is taken into account for confirmation of response:

- PR or CR needs to be confirmed at a subsequent tumor assessment, preferably at the regularly scheduled 6-week assessment interval (after 12 months of treatment, 12-week assessment interval will be used), but no sooner than 4 weeks after the initial documentation of CR or PR and before progression
- It is assumed that tumor growth is a continuous process, but due to measurement variability there might be fluctuations in tumor assessments. Therefore, confirmation of response must not necessarily be at the next scan, but could be at any subsequent scan before PD. For instance, if a subject has PR-SD-PR or PR-NE-PR at consecutive tumor assessments, the BOR would qualify for PR.
- The minimum duration for a BOR of stable disease (SD) is defined as at least 6 weeks (42 days) after randomization and before progression

The Objective Response Rate (ORR) is defined as the proportion of subjects having reached a confirmed BOR of CR or PR according to RECIST v1.1 and as per investigator assessment in the Maintenance Phase.

Table 5 summarizes the derivation rules described by [Eisenhauer, et al. \(5\)](#) for the BOR when confirmation from subsequent assessment is needed.

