5.1.2.1 Induction Chemotherapy

Subjects enrolled in this trial will start with a 12-week chemotherapy Induction Phase comprised of oxaliplatin and either 5-FU or capecitabine (according to the dosing schedule in [Section 6.2.2](#) and [Table 1](#) and [Table 2](#) or in accordance to the label instructions and per local guidelines).

- Oxaliplatin at 85 mg/m² IV on Day 1 with leucovorin 200 mg/m² IV on Day 1 (or equivalent levoleucovorin dose) followed by 5-FU at 2600 mg/m² IV continuous infusion over 24 hours on Day 1, given every 2 weeks (for up to 12 weeks, [Table 2](#)).

OR

Oxaliplatin at 85 mg/m² IV on Day 1 with leucovorin 400 mg/m² IV on Day 1 (or equivalent levoleucovorin dose) followed by 5-FU at 400 mg/m² IV push on Day 1 and 2400 mg/m² IV continuous infusion over 46-48 hours (Days 1 and 2) given every 2 weeks (for up to 12 weeks)

OR

- Oxaliplatin at 130 mg/m² IV on Day 1 with capecitabine at 1000 mg/m², twice daily for 2 weeks followed by a 1-week rest period given every 3 weeks (for up to 12 weeks, [Table 1](#)).

Local label and guidelines should be followed for specific starting doses due to renal or hepatic impairments and for subsequent dose modifications due to different toxicities.

Subjects who experience a CR, PR, or SD after 12 weeks will be randomly assigned to either avelumab or continue the same regimen of chemotherapy from the Induction Phase. Subjects who demonstrate a response during the Induction Phase that renders their measurable disease no longer measurable at the time of the Maintenance Phase can be randomized.

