5.3.1 Inclusion Criteria

For inclusion in the trial, all of the following inclusion criteria must be fulfilled:

1. Has read, understood and signed written informed consent before any trial-related procedure is undertaken that is not part of the standard subject management
2. Male or female subjects aged ≥ 18 years
3. Availability of a recently-obtained (within 6 months) biopsy from a non-irradiated area, formalin-fixed, paraffin-embedded (FFPE) block containing tumor tissue or a minimum

number of 10 (preferably 25) unstained tumor slides (cut within 1 week) suitable for PD-L1 expression assessment.

4. Disease must be measurable per RECIST v1.1
5. Subjects with histologically confirmed unresectable locally advanced or metastatic adenocarcinoma of the stomach or GEJ
6. ECOG PS of 0 to 1 at trial entry
7. Estimated life expectancy of more than 12 weeks
8. Adequate hematological function defined by white blood cell (WBC) count $\geq 2.5 \times 10^9/L$ with absolute neutrophil count (ANC) $\geq 1.5 \times 10^9/L$, lymphocyte count $\geq 0.5 \times 10^9/L$, platelet count $\geq 100 \times 10^9/L$, and hemoglobin ≥ 9 g/dL (may have been transfused).
9. Adequate hepatic function defined by a total bilirubin level $\leq 1.5 \times$ the upper limit of normal (ULN) range and aspartate aminotransferase (AST) and alanine aminotransferase (ALT) levels $\leq 2.5 \times$ ULN for all subjects
10. Adequate renal function defined by an estimated creatinine clearance ≥ 30 mL/min according to the Cockcroft-Gault formula (or local institutional standard method)
11. Negative blood pregnancy test at Screening for women of childbearing potential. For the purposes of this trial, women of childbearing potential are defined as: "All female subjects after puberty unless they are postmenopausal for at least 2 years, are surgically sterile, or are sexually inactive."

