## 14 Treatment Compliance and Exposure

*Analysis sets: Safety-Induction Analysis Set, Safety-Maintenance Analysis Set*

All dosing calculations and summaries will be based on the administration of study medications from the corresponding eCRF pages.

All subjects enrolled in this trial will start with a 12-week chemotherapy Induction Phase during which subjects receive oxaliplatin and either 5-FU or capecitabine (according to the dosing schedule in Section 6.2.2 and Table 2 in the CTP).

Subjects who experience a CR, PR, SD, or Non-CR/ Non-PD at the end of Induction Phase will be randomized to the Maintenance Phase.

**Best Supportive Care (BSC):** Best supportive care is defined as: treatment administered with the intent to maximize quality of life without a specific antineoplastic regimen.

Maintenance Phase treatment arms are as follows:

- **Avelumab arm:** Subjects randomized to the avelumab arm will receive an IV infusion of avelumab at a dose of 10 mg/kg (over the duration of 1 hour) once every 2 weeks (one cycle).
- **Chemotherapy/BSC arm:** Following the completion of the Induction Phase, site investigators will determine whether subjects are eligible to receive further chemotherapy during the Maintenance Phase. Subjects randomized to the Chemotherapy/BSC-only arm will receive the following:
  - **Oxaliplatin + 5-FU:** If subjects are deemed eligible to receive further chemotherapy and received oxaliplatin + 5-FU in the Induction Phase, they will receive the same regimen as they received in the Induction Phase, e.g. Oxaliplatin at 85 mg/m^2 IV on Day 1 plus leucovorin 200 mg/m^2 IV on Day 1 followed by 5-FU at 2600 mg/m^2 IV continuous infusion over 24 hours on Day 1, once every 2 weeks. Please refer to the CTP for alternative dosage/administration schedules.

- **Oxaliplatin + Capecitabine arm:** If subjects are deemed eligible to receive further chemotherapy and received oxaliplatin + capecitabine in the Induction Phase, they will receive the same regimen as they received in the Induction Phase, i.e. oxaliplatin at 130 mg/ m^2 IV on Day 1 with capecitabine at 1000 mg/m^2, twice daily for 2 weeks followed by a 1-week rest period once every 3 weeks.
- **BSC-Only:** Subjects who are not deemed eligible to receive further chemotherapy will receive BSC alone with no active therapy.

Analysis of exposure will be based on the calculated actual dose levels:

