The stratified odds ratio in terms of objective response (OR) will also be estimated with a Mantel-Haenszel estimator along with its 95% CI to compare the treatment effect. The odds ratio is defined as the odds of OR with avelumab divided by the odds of OR with chemotherapy. The Breslow-Day test will be used to test the null hypothesis that odds ratios in all regions are equal against the alternative hypothesis that the odds ratio in at least one region is different.

In case the null hypothesis of homogeneity of odds ratios across regions is not rejected at the alpha level of 5% two-sided, the common odds ratio will be determined as the Mantel-Haenszel estimate (by the SAS FREQ procedure using the CMH option); if the null hypothesis of homogeneity of odds ratios across all regions is rejected, the odds ratio per region will be calculated with the corresponding exact CI.

In addition, the frequency (number and percentage) of subjects with BOR of CR, PR, SD, PD, non-CR/non-PD (applicable only to subjects with non-measurable target-lesion disease at screening), and NE will be tabulated. Patients with BOR of NE will be summarized by reason for having NE status. The following reasons will be used:

---

[REDACTED]

- No post-baseline assessments
- All post-baseline assessments have overall response NE
- No post-baseline assessments due to death within 6 weeks after randomization
- No post-baseline assessments due to other reasons
- New anticancer therapy started before first post-baseline assessment
- SD of insufficient duration (< 6 weeks after date of randomization without further evaluable tumor assessment)
- PD too late (i.e. tumor assessment of PD was >12 weeks after date of randomization and there was no tumor assessment in between)
- NED maintained post Re-Baseline

Special and rare cases where BOR is NE due to both early SD and late PD will be classified as ‘SD too early’.

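### SAP 15.2.2 equates no measurable disease at Re-Baseline with complete response, so on its literal wording residual non-measurable disease that clears on maintenance is scored not evaluable

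*SAP*

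**What the plan says.** - **Who the rule covers.** SAP 15.2.2 describes the group as "Subjects without measurable disease at the Re-Baseline visit (i.e. subjects who experienced a complete response at completion of the Induction Phase".
- **What the rule does.** If later scans show no new lesions, no non-target lesions and target diameters summing to 5 mm or less, the time point is called NED, which is not an admissible BOR. The SAP concludes that "these subjects cannot achieve a BOR other than NE or PD, and these subjects will be included in the analysis as non-responders". A NED time point at 42 days or more after randomisation gives BOR = NE, with a stated reason that NED was maintained after Re-Baseline.
- **The BOR table.** Further on in SAP 15.2.2, the tabulated categories include "non-CR/non-PD (applicable only to subjects with non-measurable target-lesion disease at screening".
- **Reference scan.** SAP 10 makes the investigator's reading of the Re-Baseline scan the RECIST 1.1 baseline for the Maintenance Phase. SAP 15.2.2 repeats that response is assessed relative to that scan.
- **Who is randomised.** Protocol 5.1.2.1 says that subjects showing "a response during the Induction Phase that renders their measurable disease no longer measurable at the time of the Maintenance Phase can be randomized". Protocol 5.2.6 and 7.1.3 say the same.
- **Entry.** Inclusion criterion 4 (Protocol 5.3.1): "Disease must be measurable per RECIST v1.1".
- **ORR.** Protocol 8.3.2.2 defines it as the proportion of all randomised subjects with a confirmed BOR of CR or PR under RECIST 1.1. It contains no NED rule.

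**The concern.** A response that makes disease no longer measurable need not be complete. Lesions can shrink below the measurable threshold, or only non-target disease may remain. The protocol's permission to randomise is not limited to CR, so the group without measurable disease at Re-Baseline can hold two kinds of subject: those with nothing left, and those with residual non-measurable disease. The SAP's parenthesis merges them and applies to both a rule that makes sense only for the first.

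Two consequences follow. A subject with residual disease that disappears on maintenance could be counted as a failure in a key secondary endpoint. A subject whose residual disease simply persists has no BOR category that describes the outcome. ORR in the Maintenance Phase is a stated superiority objective and the last step of the confirmatory hierarchy, and its estimate depends directly on these derivation rules.

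**Working it through.** The documents state no ORR assumption, no power for ORR and no count of subjects without measurable disease at Re-Baseline. There is therefore no plan figure to reproduce. The check is a trace of the rules, followed by an illustration of size.

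**Trace through the rules**

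1. *Residual non-measurable disease at Re-Baseline, then clear on two scans at least 4 weeks apart, both at day 42 or later.* Relative to Re-Baseline, disease has gone from present to absent, which is a confirmed CR and a responder. On the literal wording of SAP 15.2.2, the subject had no measurable disease at Re-Baseline and each scan meets the NED definition, so BOR = NE and the subject is a non-responder. The recorded reason, that NED was maintained, would be untrue because disease was present at Re-Baseline.
2. *Residual non-measurable disease that persists without progression.* Relative to Re-Baseline this is non-CR/non-PD. The BOR table closes that row because disease was measurable at screening. Table 5 has no line for it, and none of the listed NE reasons describes it. ORR does not change, because the subject is a non-responder either way.
3. *True CR at Re-Baseline that stays clear.* NED, then NE. There was nothing left to respond, so no response is lost.

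Only case 1 changes ORR. Case 2 changes only the BOR table.

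**Size of case 1**

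Inputs: N = 499 randomised (Protocol 8.1); f = share with residual non-measurable, non-CR disease at Re-Baseline (assumed 2% to 15%); c = share of these whose disease then clears (assumed 5% to 30%).

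ORR loss = f × c; responders lost = 499 × f × c.

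- f = 2%, c = 5%: 0.02 × 0.05 = 0.1 points; 499 × 0.001 = 0.5 subjects
- f = 5%, c = 10%: 0.05 × 0.10 = 0.5 points; 499 × 0.005 = 2.5 subjects
- f = 10%, c = 20%: 0.10 × 0.20 = 2.0 points; 499 × 0.020 = 10.0 subjects
- f = 15%, c = 30%: 0.15 × 0.30 = 4.5 points; 499 × 0.045 = 22.5 subjects

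**Effect on the comparison**

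f is fixed before randomisation, so it is expected to be equal in the two arms. The change in the ORR difference is f × (c avelumab − c control), which is zero when clearance is equal. With f = 10% and assumed clearance of 20% against 10%, it is 0.10 × 0.10 = 1.0 point.

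**The case against.** The best defence is that the parenthesis limits the rule to complete responders. The NE reason speaks of NED being maintained, which fits only a subject already free of disease at Re-Baseline. The version history in SAP 4.1 also describes the handling as meant for subjects with CR at Re-Baseline. On that reading a subject with residual disease falls under the general RECIST rule, and a confirmed CR counts. This is probably the intent. It does not repair the operative sentence, which defines its group by absence of measurable disease and uses a NED definition that cleared residual disease also meets. Nor does it touch the screening tie.

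Other parts of the defence stand, and they rule out stronger readings that a reader might infer:

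- *That every subject without measurable disease loses a response.* The rule is conditional on a later clear scan, and true CRs lose nothing.
- *That ORR is capped.* Taking the 15% ORR in Protocol 5.2.3 and an assumed 5% to 15% without measurable disease gives 15% × 0.95 = 14.25% down to 15% × 0.85 = 12.75%. That is dilution by true CRs in the denominator as well as by the subset at issue, and limiting the rule to CRs would leave the CR part in place. The 15% is also a general avelumab figure, not a maintenance ORR against a post-chemotherapy baseline.
- *That SAP 14 proves the subset exists.* It says "Subjects who experience a CR, PR, SD, or Non-CR/ Non-PD at the end of Induction Phase will be randomized", but the SAP's only stated scope for that label is non-measurable disease at screening, so the line is consistent with the BOR table. The evidence for the subset is the protocol's randomisation wording.
- *That the non-CR/non-PD row must be empty.* BOR is tabulated in all randomised subjects, and SAP Appendix I has a deviation code for entry without measurable disease. The row is near-empty by design, not impossible.

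**Conclusion.** The point holds as a wording and derivation defect. On the literal text of SAP 15.2.2, residual non-measurable disease that clears on maintenance is scored NE and non-responder, although the SAP's own reference scan makes it a CR once confirmed. Persistent residual non-measurable disease has no correct BOR category, which leaves ORR unchanged.

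The size is unknown. The figure of 0.1 to 4.5 ORR points (0.5 to 22.5 of 499 subjects) rests entirely on assumed f and c, and is zero if the programmers apply the narrower reading. The rule uses a pre-randomisation status and is identical in both arms, so it would lower ORR in both and shift the comparison only if clearance differs by arm. The documents do not support a claim that the treatment comparison is biased.

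ORR is tested only after both OS hypotheses and PFS are rejected (Protocol 8.5.1, SAP 15), and Protocol 8.1 already expects less than 80% power for OS in PD-L1+ subjects. OS is unaffected. The correction should be made, but it does not bear on the trial's primary conclusion.

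**What to change.** In SAP 15.2.2:

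1. Restrict the NED-to-NE rule to subjects with CR at Re-Baseline per investigator, and remove the equation of that group with absence of measurable disease.
2. State that subjects with residual non-measurable disease at Re-Baseline are evaluated as CR, non-CR/non-PD or PD relative to that scan, with a confirmed CR counting in ORR.
3. In the BOR tabulation, define the non-CR/non-PD category by disease status at Re-Baseline instead of at screening.

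It would help to report by arm how many subjects had CR and how many had residual non-measurable disease at Re-Baseline, since that shows whether the issue matters in practice. A supportive ORR restricted to subjects with disease present at Re-Baseline is optional; because that status precedes randomisation, the comparison would remain randomised.

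The cost is a few lines of SAP text and a derivation change using Re-Baseline scan data already required for randomisation. No new data are needed.

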Additionally, subjects receiving avelumab who have experienced a CR should be treated for a minimum of 12 months or until disease progression or unacceptable toxicity, after confirmation of response. In case a subject with a confirmed CR relapses after stopping treatment, but prior to the end of the trial, 1 re-initiation of treatment is allowed at the discretion of the Investigator and after agreement with the Medical Monitor. In order to be eligible for retreatment, the subject must not have experienced any toxicity that led to treatment discontinuation of the initial avelumab therapy. Subjects who re-initiate treatment will stay on trial and will be treated and monitored according to the protocol and follow the Schedule of Assessments until disease progression (see [Table 3](#)).

The treatment should start within 4 days after randomization. While on trial treatment, subjects will be asked to visit the trial site as specified in the Schedule of Assessments (see [Table 3](#), [Table 4](#), [Table 5](#), and [Table 6](#)).

For both avelumab and maintenance chemotherapy, a time window of up to 4 days before or 2 day after the scheduled visit day (-4/ +2 days) will be permitted for all trial procedures. Subjects should return to the target date even if the previous visit was off schedule.

The tumor evaluation (see [Section 7.3](#)) will be performed every 6 weeks (for the first 12 months and every 12 weeks thereafter) with a time window of -5 days for both avelumab and maintenance chemotherapy.

Subjects will receive either:

- Avelumab by IV infusion following pretreatment (see [Section 5.1.2.2.1](#)) once every 2 weeks (see [Section 6.2.1](#)), or
- Maintenance chemotherapy following pretreatment as applicable prior to each infusion (see [Section 6.2.2](#)).

Assessments to be performed during the Maintenance Phase are presented in [Table 3](#) to [Table 6](#).

During the treatment period, the following assessments and procedures will be performed (see [Table 3](#) to [Table 6](#) for the detailed schedule):

- The subject-reported outcomes/QoL assessments will be completed by subjects prior to any trial-related procedures (time points outlined in [Table 3](#) to [Table 6](#)) and then every 6 weeks thereafter.
- AEs and concomitant medications and procedures will be documented at each visit.
- ECOG PS will be assessed at each treatment visit.

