8.3.2.2 Best Overall Response

Best Overall Response in Maintenance Phase is the key secondary endpoint for the study. The confirmed BOR will be determined according to RECIST v1.1, per Investigator assessment, and statistically evaluated as the ORR. BOR is defined as the best response obtained among all tumor assessment visits after the date of randomization until documented disease progression.

For a BOR of PR or CR, confirmation of the response according to RECIST v1.1 will be required, preferably at the regularly scheduled 6-week assessment interval but no sooner than 4 weeks after the initial documentation of CR or PR. Confirmation of PR can be confirmed at an assessment later than the next assessment after the initial documentation of PR. A BOR of SD requires that an overall response of SD has been determined at a time point at least 6 weeks after randomization.

The ORR is defined as the proportion of all randomized subjects with a confirmed BOR of PR or CR according to RECIST v1.1, as per Investigator assessment.

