**Definition of duration:**

Duration will be calculated by the difference of start and stop date + 1, if not otherwise specified. For example, survival time (days) = date of death – date of randomization + 1.

The time since an event (e.g. time since first diagnosis) will be calculated as reference date minus date of event.

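### The 42-day minimum for a best response of SD ignores the 5-day early scan window, so a compliant first scan can be rejected as too early; only the descriptive BOR table is affected

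*SAP*

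**What the plan says.** **Response rule.** SAP 15.2.2: "The minimum duration for a BOR of stable disease (SD) is defined as at least 6 weeks (42 days) after randomization". Protocol 8.3.2.2 has the same rule: "A BOR of SD requires that an overall response of SD has been determined at a time point at least 6 weeks after randomization". Neither mentions a tolerance.

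**Scan timing.** Protocol 7.1.4 says of the on-treatment scans that they "will be performed every 6 weeks (for the first 12 months and every 12 weeks thereafter"). The tolerance that it attaches to this schedule is stated separately in the sentence: "with a time window of -5 days for both avelumab and maintenance chemotherapy". No days after the target are given for these scans.

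**Start of treatment.** The same section says: "The treatment should start within 4 days after randomization". The visible text does not say whether the first 6-week scan is counted from randomization or from first dose.

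**Day count.** SAP section 10: "Duration will be calculated by the difference of start and stop date + 1, if not otherwise specified". SAP 15.2.2 does not say whether its 42-day check follows this convention.

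**When the minimum is missed.** The NE reasons listed after SAP Table 5 include "SD of insufficient duration (< 6 weeks after date of randomization without further evaluable tumor assessment"). In Table 5, an unconfirmed CR or PR followed by PD counts as SD only if the minimum is met, and as PD otherwise. Table 5 has no row with SD as the first response.

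**The concern.** The scan schedule and the response definition use the same nominal 6 weeks, but only the schedule has a tolerance, and that tolerance runs towards early scans. A site can scan on time under protocol 7.1.4 and still produce a scan that SAP 15.2.2 treats as too early to support SD. Such a scan is not a deviation either: for scan timing, SAP Appendix I lists 6-weekly scans more than 10 days outside the window.

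Two subjects with the same disease course can then be reported differently. Take two subjects who are stable at the first scan and have no further evaluable scan, with the 42-day check made on elapsed days. The one scanned on Day 42 is SD and the one scanned on Day 40 is NE. What is at stake is the planned frequency table of BOR categories (SD, PD, NE) and the breakdown of NE reasons.

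**Working it through.** **Inputs**
- Minimum for SD: 6 weeks after randomization (protocol 8.3.2.2); 42 days (SAP 15.2.2).
- First scan due at 6 weeks, window -5 to 0 days (protocol 7.1.4).
- Shift if scans are counted from first dose: 0 to 4 days after randomization (protocol 7.1.4).
- Day count: elapsed days, or the SAP convention of difference plus 1 (SAP section 10).

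**Step 1. The plan's own figure.** 6 × 7 = 42 days, which agrees with SAP 15.2.2.

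**Step 2. Permitted first-scan days.** With the schedule anchored *k* days after randomization, the permitted days after randomization run from 42 + *k* − 5 to 42 + *k*, six days in all. A day *d* fails if *d* < 42 (elapsed) or *d* + 1 < 42 (plus-1 count).

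| Anchor *k* | Permitted days | Fail, elapsed | Fail, plus 1 |
|---|---|---|---|
| 0 | 37–42 | 5 of 6 | 4 of 6 |
| 1 | 38–43 | 4 of 6 | 3 of 6 |
| 2 | 39–44 | 3 of 6 | 2 of 6 |
| 3 | 40–45 | 2 of 6 | 1 of 6 |
| 4 | 41–46 | 1 of 6 | 0 of 6 |

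At least one compliant day fails in 9 of the 10 combinations. The range is 0 to 5 of 6. These are shares of calendar days, not of subjects.

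**Step 3. The general visit window.** Protocol 7.1.4 also gives -4/+2 days for trial procedures in general. Anchored at randomization, that permits Days 38–44, of which Days 38–41 (4 of 7) still fall below 42 elapsed days.

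**Step 4. From scan days to subjects.** A subject's category changes only if the first scan is early and no later scan shows SD or better before PD. The documents give neither the distribution of scan days nor the progression rate between scans. As an illustration only, assume exponential progression with a median of *m* months. The share of subjects with SD at the first scan who progress within the next 42 days is 1 − 2^(−(42/30.4375)/*m*):
- *m* = 2: 38%
- *m* = 3: 27%
- *m* = 4: 21%
- *m* = 6: 15%

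This bounds one ingredient. It does not estimate the number affected, because the share of first scans done early is unknown.

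**Step 5. The minimum reduced by the window.** 42 − 5 = 37 days. With 37 in place of 42, all 6 permitted days pass for every anchor from 0 to 4 and under both day counts.

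**The case against.** The strongest defence is that there is no error. Protocol and SAP state the same rule. A scan window governs visit compliance, a minimum duration governs what counts as stable disease, and nothing in the documents requires the second to be reduced by the first. The NE cases are also disclosed, since NE is tabulated by reason. This stands to the extent that the rule is internally consistent and can be applied as written. It does not remove the effect: the category reported can depend on the scan day within the permitted window.

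Several stronger readings are tempting but not supported:
- **That a key secondary endpoint is compromised.** Protocol 8.3.2.2 evaluates BOR statistically as ORR, which counts confirmed CR or PR only. The CMH test, the odds ratio and the subgroup logistic model do not distinguish SD from PD or NE.
- **That disease control rate is distorted.** The SAP's abbreviation list includes the term, but no such analysis is visible in the unredacted text.
- **That five in six first scans would be misclassified.** That is the worst case for scan days (anchor at randomization, elapsed days). Turning it into a share of scans needs an even spread that the documents do not support, and a later SD scan before PD restores SD.
- **That SD followed by PD is explicitly scored as PD.** This is inferred from the CR–PD and PR–PD rows of Table 5. The NE outcome is explicit.
- **That the 42-day cut for no evidence of disease (NED) under-counts SD.** Under SAP 15.2.2 those subjects can only be NE or PD, so it cannot.
- **That one arm is favoured.** The window is the same for both arms. A difference would need unequal scan timing or early progression, which the documents do not show.

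The response-assessment rows of the schedule tables are redacted and may state the anchor, so the point rests on the text of protocol 7.1.4.

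**Conclusion.** The point holds as a cheap improvement to a descriptive table. A first on-treatment scan done within the protocol window can miss the SD minimum, and the subject may then be tabulated as NE, or as PD where PD follows. Between 0 and 5 of the 6 permitted days fail. The conflict disappears only at the far end of the range examined, where scans are anchored 4 days after randomization and the plus-1 count is used. The number of subjects affected cannot be derived from the documents. No hypothesis test, alpha allocation or ORR estimate changes.

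The conclusion assumes that the -5 day window in protocol 7.1.4 applies to the first maintenance scan and that treatment starts within 4 days of randomization, as that section asks.

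**What to change.** Set the minimum for a BOR of SD to 6 weeks minus the scan window, that is 37 days after randomization. State whether the 6-week scan is counted from randomization or first dose, and whether the minimum uses elapsed days or the plus-1 count. Make the same change in three places: protocol 8.3.2.2, the minimum-duration rule in SAP 15.2.2, and the NE reason for SD of insufficient duration later in that section. Changing the 42-day NED cut in SAP 15.2.2 is optional, for consistency only, because it cannot alter the SD count.

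One limit remains. Protocol 7.1.7 gives off-treatment scans a window of ±1 week, so a first scan at Day 35 or 36 would still fall short of 37 days. The SAP should say whether that is intended.

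The cost is a few lines of text and one programmed constant, with no change to visits, data collection or alpha. It should be made before database lock. Protocol 8.5.1 lets the SAP modify the planned analyses and reserves amendments for major changes, so a line in SAP section 8 could record the departure from protocol 8.3.2.2 if no amendment is otherwise planned.
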